7.2. Blood sample collection

For patients enrolled in the randomization arm, blood drawn for research purposes will be collected at the patient's standard of care blood draws whenever possible, which should result in only one additional venipuncture being necessary (at the Week 6 visit). Lab results from the research samples will be entered into the patient's chart and reported to the patient. About 15 mL (one tablespoon) of additional blood will be taken; no research samples will be saved or banked for future testing. No additional blood for research purposes only will be drawn from patients enrolled in the standard of care arm.

7.3. Data entry

Data will be collected electronically and on paper. The following will be captured electronically: (1) data from the electronic medical record (see data collection sheet); (2) voice and swallow evaluation video and audio recordings and clinician reports/summaries; (3) audio recordings of participant interviews and electronic codes for content themes. Paper data collection will consist of the QOL instruments (SF12, EAT-10, EORTC, ThyCa-QOL, and VHI). Raw data will be scored or otherwise evaluated as necessary and entered into a study-specific Microsoft Access database as soon as possible after data collection.

Voice and videostroboscopy recordings collected during this study may not be immediately destroyed after all research procedures have been completed, as this data could be of value to a follow up or related study. IRB approval will be sought for any use of this data outside of the study parameters described in this protocol.

7.5. Stopping rules (By the Data Safety and Monitoring Committee)

The DSMC shall have authority to stop a research protocol in progress and remove individual human participants from a research protocol. The Data Safety and Monitoring Committee may request enrollment be suspended due to safety concerns.

8. Data analysis and statistical considerations

8.1. Sample size determination

At the beginning of this study, we anticipated randomizing 140 patients with clinically node negative thyroid cancer, with the goal of 116 participants completing the study. Patients will be recruited from the Endocrine Surgery and Otolaryngology Clinics at the University of Wisconsin Hospitals and Clinics. This is a high volume tertiary care center with a large thyroid practice, performing approximately 350 thyroid operations per year. Thyroid cancer accounts for 30% of thyroidectomy cases at our institution and this is the pool from which the patients will be identified (approximately 105 patients/year). Approximately 15% of thyroid cancer cases will have a positive pre-operative ultrasound, thus decreasing our pool of eligible participants to approximately 89 patients per year. With an accrual goal of 140 participants within 4 years, we would need to recruit 39% of eligible patients each year.

Permanent complications in thyroid surgery are uncommon, but these complications can be disastrous for a patient that is affected. Permanent hypoparathyroidism occurs in 1-2% of patients after a total thyroidectomy and the risk may be as high as 14% when a CND is performed. The best surrogate marker to predict an increase in permanent morbidity is the incidence of transient hypoparathyroidism, which is substantially more common than permanent hypoparathyroidism. For example, transient hypoparathyroidism occurred in 12% of our last 270 patients undergoing a total thyroidectomy. The rate of transient hypoparathyroidism in patients treated with a CND has been shown in the literature to be significantly higher. The rate of transient hypoparathyroidism in recent large retrospective studies was reported to be between 38-51%.

We assumed a power of 0.8 and an alpha of 0.05. For sample size calculations we made the assumption that the incidence of transient hypoparathyroidism after a total thyroidectomy alone is 12% and that an increase to 36% (or tripling of the risk) is clinically significant. The rate of hypoparathyroidism in Arm 1 is based upon our last 270 patients and is a reliable estimate. The incidence in the CND arm is based on a

review of the literature and we purposely chose a number on the lower end of quoted ranges to ensure that we are not underestimating our sample size. With these assumptions the sample size is 116, with 58 patients per arm. Due to the short follow up for our primary endpoint (post-operative day 1) and for our secondary endpoints (<12 months), we anticipate no significant loss to follow up. For our secondary aims, we chose the Dysphonia Severity Index (DSI) as representative and found a prior thyroid surgery study (45) showing that as few as 8 patients in a negative voice outcome group were sufficient to detect clinically meaningful differences on this measure versus patients with normal vocal functioning at 6 months post-op. Thus, the sample size in our study should be adequate to address our secondary aims even if there is attrition/ loss to follow-up.

The number of patients who must be consented will be larger than the final sample size because a portion of patients that are enrolled and evaluated pre-operatively may not be randomized the day of surgery (because malignancy is not proven intraoperatively, suspicious adenopathy is identified, or there is gross local invasion). We aim to increase the sample size by 20% to accommodate for this.

We have found in our examination of preliminary data that our objective measures are not effectively capturing the impact of surgery on patients and that the most critical and meaningful data that we are obtaining from our study is from the in-depth patient interviews. Given the value of our qualitative data, we need to ensure that we are capturing adequate qualitative data to identify differences between the objective and patient-reported evaluations of experiences with hypocalcemia and voice and swallowing problems caused by transient or permanent nerve injury. Ultimately, we plan to make our existing study aims even more robust by incorporating both objective and subjective data into each of our primary and secondary outcomes measures.

Based on our experience with qualitative research and the rates of objective complications in the patients enrolled to date, we've determined that we need to enroll at least 62 patients in order to obtain an adequate dataset to examine the impact of hypocalcemia and 70 patients in order to obtain an adequate dataset to examine the impact of vocal cord dysfunction. While we will continue to recruit as many patients as feasible, based on these calculations, if we are able to enroll at least 70 patients, this should give us the data necessary to evaluate all of our study aims.

Therefore, we will plan to randomize 70 - 140 patients. We will plan to recruit patients up until year 5 of the study as the primary recurrence endpoint will be at 1 year. Given the fact that we anticipate having at least 89 eligible patients per year, we should meet our recruitment goal while allowing for at least 1 year of follow up in all study patients.

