In this clinical trial, 70 - 140 patients undergoing surgery treatment for thyroid cancer will be enrolled into one of three treatment arms. Patients receiving total thyroidectomy for papillary thyroid cancer (PTC) with no pre-operative evidence of distant or cervical lymph node metastasis will be randomized into one of two arms: prophylactic central neck dissection or no central neck dissection. Patients who are not eligible for randomization will be enrolled into a third standard of care arm. We will then compare the three cohorts: (1) To determine the rate of transient and persistent hypocalcemia; (2) To determine the rate of voice and swallowing problems; (3) To determine the degree to which HR-QOL is compromised; (4) To determine clinical recurrence rates; (5) To determine the degree to which Natural Language Processing (NLP) tools can extract and document quality of life measures from patient interview narratives; (6) To determine the extent of correlation among quality of life measures obtained from patient interview narratives and those from traditionally administered quality of life surveys.

Figure 1: Trial overview diagram

Schedule of activities

	Visit 1	Visit 2	Visit 3	Visit 4	Visit 5		Visit 6	Visit 7	
	Screening	Day of Operation	Post-Op	Day 12	Week 6	Cancer Screen	Month 6	1 Year	Follow-up
Window	6 weeks-24 hours before operation		0-2 days	± 8 days	4-20 weeks	+2-7 days after Week 6	±6 weeks ¹	10 – 18 months	+10-19 months (+1-6 weeks post 1 year)
Informed Consent Obtained	X								
Venipuncture	SOC		SOC	SOC	SOC	SOC ^{2, 3, 4}	CI	SOC	
Calcium ³	SOC ³		SOC ^{3, 5}	SOC ^{3, 5}			X ^{5, 17}	CI ^{5, 17, 18}	
Parathyroid Hormone (PTH) ³	SOC ³		SOC ^{3, 5}	SOC ^{3, 5}			X ^{5, 17}	CI ^{5, 17, 18}	
Vitamin D ¹⁷	CI ^{6, 17}								
Neck Ultrasound	SOC ⁷						SOC	SOC	
Chest X-ray ⁸	SOC ⁸								
Comprehensive Voice Evaluation: Phonation Threshold Pressure, Dysphonia Symptom Index, CAPE-V, GRBAS, Stroboscopy, Glottal Function Index, VHI	CI ⁹			CI ⁹	CI ¹⁰		CI ¹⁰	CI ¹⁰	
Swallow Evaluation: standardized videofluoroscopic swallow study ¹⁵	X ¹¹			CI ¹¹	CI ¹¹		CI ¹¹	CI ¹¹	
Quality of Life Surveys, including: (1) the Short Form 12 (SF-12, Medical Outcomes Trust); (2) The European Organization for Research and Treatment of Cancer QOL instrument (EORTC QLQ C30); (3) The Voice Handicap Index (VHI) for assessing voice-related QOL (part of voice evaluation); (4) the EAT-10 Swallow Instrument; (5) Thyroid Cancer QOL (Thy-Ca QOL)	X			X	X		X	X	

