Operative Procedure: Total thyroidectomy will be performed using standard techniques in all patients potentially eligible for randomization. An open technique will be used to remove the entire thyroid including pyramidal lobe and all visible thyroid tissue. Care will be taken to visualize and preserve both recurrent laryngeal nerves and to preserve all parathyroids in situ. All removed specimens will be carefully examined for any parathyroid tissue and any devascularized or resected normal parathyroid glands will be confirmed by frozen section and autotransplanted into the sternocleidomastoid muscle.

For randomization patients who do not have a pre-operative diagnosis confirming PTC, a frozen section of the suspicious nodule(s) will be performed intra-operatively. If frozen section confirms PTC, the surgical procedure will continue and the patient will be randomized. If frozen section does not confirm cancer, randomization will not occur, and the operative procedure will continue according to clinical indication. During surgery, unexpected and suspicious lymphadenopathy will be biopsied. If lymph node metastases are found, then a CND would be performed at the discretion of the treating surgeon, and the patient will not be randomized. If lymph node metastases are not found in the biopsy, and the surgeon would not otherwise perform a CND based on the observed suspicious lymph node, the participant will be randomized per protocol. Once a patient has met both pre-operative intra-operative inclusion criteria and the randomization envelope is opened, he or she is enrolled in the study. Patients who screen fail intraoperatively will continue their participation with the study as part of the standard of care arm.

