6.3. Recruitment and consent

The human subjects participating in this study will be recruited from the University of Wisconsin Endocrine Surgery and Otolaryngology Clinics as well as patients referred to the clinic by regional endocrinologists. A participant's decision whether or not to participate will not affect the care he or she receives as a patient. Participants will be treated according to the standard of care for their disease until

consent for the study is obtained. Participants must meet inclusion and exclusion criteria as listed above. Participants will be selected without consideration of socio-economic background or insurance status.

Following explanation of the consent form, each potential participant will be given an opportunity to read it thoroughly. Before being allowed to sign the consent form, potential participants also will be given an opportunity to ask questions. The investigator will emphasize the fact that the participant can terminate involvement at any time without any consequences. Once the consent form has been signed, the study pre-operative procedures will be performed if not already captured in the medical record.

7. Activities and measurements

Enrollment: Participants will be enrolled after signing the informed consent form.

Pre-operative visit: The pre-operative visit will include a study-required baseline assessment of every participant's voice and swallow⁵ function and a QOL survey. A baseline assessment of vocal function will be considered clinically indicated in those patients with existing voice complaints or prior neck surgery. If patients are found to have some abnormality on their vocal evaluation that would warrant intervention, they will not proceed to randomization. These pre-operative study evaluations will be coordinated with the standard collection of the participant's pre-operative medical history, physical exam, and laboratory evaluation.

Day of surgery: Once the surgeon visually confirms there is no evidence of nodal involvement intraoperatively, the participant will be randomized. Study arm randomization will be computer generated by [name] of the UW Department of Surgery Biostatistics Office and communicated to the surgeon via sealed envelope. Participants will be blinded to their treatment arm until the Day 12 visit.

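### The 70-140 target has no single counting unit, and the 80% power belongs to 116 randomised patients and does not carry over to the floor of 70

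*Combined protocol and SAP*

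**What the plan says.** Section 8.1 fixes the design inputs: "We assumed a power of 0.8 and an alpha of 0.05", with transient hypoparathyroidism in 12% after total thyroidectomy alone and 36% with central neck dissection. From these it obtains 116 patients, 58 per arm.

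The recruitment target is then described in several ways:

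- **Randomised, with fewer completing.** Section 8.1 opens with "we anticipated randomizing 140 patients with clinically node negative thyroid cancer, with the goal of 116 participants completing the study".
- **Consented.** Later in 8.1, the 20% uplift is justified because "a portion of patients that are enrolled and evaluated pre-operatively may not be randomized the day of surgery". Attrition is not the reason, since for the primary and secondary endpoints "we anticipate no significant loss to follow up".
- **Randomised, as a range.** 8.1 concludes "we will plan to randomize 70 - 140 patients". One sentence before the end of the preceding argument, the minimum of 70 is a number to enrol.
- **Enrolled across three arms.** The Summary states "70 - 140 patients undergoing surgery treatment for thyroid cancer will be enrolled into one of three treatment arms", and Section 1.2 repeats this. The third arm is standard of care and is not randomised.

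The term enrolled does not settle the unit. Section 7 says "Participants will be enrolled after signing the informed consent form", and Section 6.2 also places enrolment before surgery. Section 3 (Operative Procedure) says that once "the randomization envelope is opened, he or she is enrolled in the study".

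The floor of 70 comes from a judgement about qualitative data: 62 patients for hypocalcemia and 70 for vocal cord dysfunction. Section 8.1 adds that 70 should be enough to evaluate all the study aims. No power is given for 70.

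**The concern.** The stated hypothesis, a higher complication rate with prophylactic dissection, is tested only by Arm 1 against Arm 2. A patient in the standard of care arm adds nothing to that comparison. Under Section 3, patients who fail screening during the operation continue in that arm, so the very patients the 20% allowance was meant to cover would also count towards a three-arm total.

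The target therefore does not tell the trial team how many randomised patients they are aiming for. Read as in the Summary, the minimum could be met with fewer than 70 in the randomised comparison. Read as in 8.1, it is met with 70, which is 46 fewer than the 116 on which the power rests. In either case a null result on hypoparathyroidism could be taken as reassurance about dissection when the trial had a modest chance of detecting a tripling of risk.

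**Working it through.** **Inputs (Section 8.1):** p1 = 0.12, p2 = 0.36, difference 0.24, mean 0.24, alpha 0.05, power 0.80, equal arms. Sidedness and test are not stated; two-sided is assumed.

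**1. Reproduce the plan's 116.** The uncorrected formula is

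n = [1.960·√(2·0.24·0.76) + 0.842·√(0.12·0.88 + 0.36·0.64)]² / 0.24² = (1.1838 + 0.4878)² / 0.0576 = 48.5, so 49 per arm (98 in total).

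With the continuity correction,

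n′ = (48.51/4)·[1 + √(1 + 4/(48.51·0.24))]² = 56.5, so 57 per arm (114 in total).

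This is within two patients of 116. One-sided versions give 78 or 94 and do not fit. The 116 is therefore sound for a two-sided, continuity-corrected comparison of two randomised arms.

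**2. Find the unit of 140.** 116 × 1.20 = 139.2, which rounds up to 140. The reason given for the 20% is consented patients who are not randomised. Two other explanations for the gap between 140 and 116 are closed off: Section 8.1 expects no material loss to follow-up, and Section 7.4 replaces participants who withdraw before Day 12. The 8.1 feasibility sum also treats 140 as accrual: 140/4 = 35 a year, and 35/89 = 39% of a pool reduced only for positive pre-operative ultrasound, not for intraoperative failures. So 140 behaves as a consent count with 116 to be randomised, although the opening sentence calls it randomised. This is an inference, and it concerns 140 only.

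**3. Power under each reading.** Every pair of event counts was enumerated under the two binomial distributions, and the probabilities of pairs significant at two-sided 0.05 were summed. Results are Fisher exact / uncorrected chi-square.

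| Reading of the target | Randomised out of 70 | Power | Randomised out of 140 | Power |
|---|---|---|---|---|
| All randomised (8.1) | 70 | 57% / 66.5% | 140 | 90% / 93% |
| Consented, share 116/140 randomised (assumption) | 58 | 46% / 58% | 116 | 83% / 88% |
| Three arms of equal size (assumption) | about 46 | 38% / 50% | about 94 | 72% / 80% |

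For the second row, 70 × 116/140 = 58. For the third, 70/3 is about 23 per arm and 140/3 about 47 per arm. The documents give no standard of care share, so the last two rows show a range and are not forecasts.

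**The case against.** Several stronger readings are tempting, and the documents do not support them.

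- **That the 80% power attaches to no defined number.** It does attach to one. Section 8.1 links it directly to 116 patients, 58 per arm, and arms in that comparison arise only by randomisation.
- **That the plan claims 80% power at 70.** It does not. The power is a past-tense design input, and the floor has a separate, qualitative rationale.
- **That recruitment will stop at 70.** Section 8.1 says recruitment continues as far as feasible. Seventy is a minimum.
- **That 70-140 is stated as a number consented.** No section says so. The explicit units are randomised and all three arms.

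It can also be said that the enrolment conflict is narrow: Sections 6.2 and 7 and the schedule of activities separate enrolment from randomisation, and the Section 3 sentence is the outlier. And the shortfall at 70 exists even if every one of the 70 is randomised, so that part comes from lowering the floor without restating power and not from mixed units.

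All of this stands, and it limits the point. It does not remove it. The Summary and Section 1.2 contradict 8.1 in plain words, 140 is called randomised but built as consented, and the statement that 70 serves all aims covers the primary aim without any power to back it.

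**Conclusion.** The point holds as an inconsistency in the target together with an unpowered floor. The 70-140 range is counted as randomised in Section 8.1 and across three arms in the Summary and Section 1.2; the derivation of 140 implies a consent count. The number supporting 80% power is 116 randomised, and the range as written does not guarantee it.

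At the floor, power for 12% versus 36% is at best 57% (Fisher) or 66.5% (uncorrected chi-square), against 83% or 88% at 116. It falls further if some of the 70 are not randomised, for example to 46% or 58% with 58 randomised. These figures assume two-sided 0.05, equal arms and the plan's own event rates. The figure of 58 also assumes that the 116/140 ratio applies to the floor, which the documents do not say.

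**What to change.** - In the Summary, Section 1.2 and Section 8.1, state the target as the number of patients randomised to Arms 1 and 2. Give the number to be consented and the number expected in the standard of care arm as separate counts.
- In 8.1, say whether 140 is consented or randomised, so that it agrees with the reason given for the 20%.
- Use one definition of enrolled in Sections 3, 6.2, 7 and 8.1.
- State that the 80% power refers to 116 randomised, name the test and sidedness, and print the power at 70 randomised.
- Qualify the statement that 70 patients are enough for all aims: the stated basis is the qualitative data, and the randomised comparison of transient hypoparathyroidism has lower power at that size.

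The cost is wording only. No procedure or data collection changes, but the power reported at the lower bound will look less favourable.

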2.1. Primary outcome and endpoints

To determine the rate of transient and permanent hypocalcemia:

- Transient hypoparathyroidism as defined by a Day 1 serum parathyroid hormone (PTH) level of <10 pg/ml
- Post-operative serum calcium (mg/dL) and PTH (pg/ml) at Day 12 and Month 6

- Total calcium consumption in first 2 weeks (total gm)
- Hypocalcemia symptoms in first 2 weeks (average episodes/day)
- Hypocalcemia symptom severity scale (range of 1-5)
- Requirement for calcium and calcitriol at Month 6 (or, if laboratory values at visit reveal calcium < 8 mg/dL and PTH <15 pg/ml)

Calcium and PTH levels, calcium intake, and hypocalcemia symptoms will be monitored post-operatively (at Day 1, Day 12, and Month 6) to examine how parathyroid function is affected by a CND.

Hypoparathyroidism can lead to paresthesias and muscle cramps and is a known complication of total thyroidectomy, requiring frequent treatment with calcium and vitamin D. This risk is increased with a CND and is thus important to quantify when examining the risk/benefit ratio. Because calcium supplementation is routinely administered for symptoms of hypocalcemia in the post-operative period and this may impact the interpretation of laboratory evaluations, we will be evaluating a variety of metrics to assess the incidence and impact of hypocalcemia on patients.

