Patients randomized to Arm 2 will be receive total thyroidectomy with an ipsilateral CND. The CND will be performed as described by a consensus conference of the ATA. This will include removal of the prelaryngeal nodes, the pretracheal nodes, and the paratracheal lymph nodes. The paratracheal dissection will be bounded superiorly by the cricoid cartilage and inferiorly by the innominate artery on the right and on the left by the axial plane where the innominate crosses the trachea. The superior parathyroid gland will be preserved in situ along with its primary blood supply from the superior branch of the inferior thyroid artery. The inferior parathyroid gland will be reflected laterally along with its blood supply from the inferior thyroid artery. Parathyroid autotransplantation will be performed if the glands are devascularized during dissection. Paratracheal tissue specimens will be examined for parathyroid glands that may be salvaged and transplanted before being removed from the sterile field. Suspected parathyroid glands will be confirmed by frozen section biopsy prior to autotransplantation.

Blinding: Both surgical procedures are performed through the same incision and post-operative care is identical. As such, the neck dressings are identical, allowing both the patients and study staff to be masked with regard to treatment arm randomization. Participants will remain blinded to treatment arm until the Day 12 follow-up appointment, at which point their pathology report will be reviewed with them, and unblinding will occur. Because subjective symptoms and calcium intake are two of our secondary endpoints, we will minimize participant and researcher bias in the description and treatment of post-operative symptoms in the immediate post-operative period. Because the risks of the two procedures and the post-operative instructions are identical for both arms, there is no risk associated with blinding the patients until their Day 12 follow-up. Participants who screen fail intra-operatively will be notified as to which procedure(s) was conducted immediately following surgery. The surgeon performing the procedure cannot and will not be blinded to the participant's treatment arm at any time.

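### Section 8.1 announces, after a look at trial data, that subjective data will be built into every primary outcome measure, which sections 2.1 and 8.2 do not define or support

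*Combined protocol and SAP*

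**What the plan says.** Section 8.1 first sizes the trial on one objective endpoint, transient hypoparathyroidism, assumed at 12% after thyroidectomy alone and 36% with central neck dissection. That gives 116 patients, 58 per arm, and the section describes the primary endpoint as falling on post-operative day 1. Section 2.1 defines it: "Transient hypoparathyroidism as defined by a Day 1 serum parathyroid hormone (PTH) level of <10 pg/ml".

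Later in section 8.1 the plan changes direction. It states: "We have found in our examination of preliminary data that our objective measures are not effectively capturing the impact of surgery on patients". It adds that "the most critical and meaningful data that we are obtaining from our study is from the in-depth patient interviews". From this it draws the intention of "incorporating both objective and subjective data into each of our primary and secondary outcomes measures".

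The next paragraph derives new minimum numbers, 62 for hypocalcemia and 70 for vocal cord dysfunction: "Based on our experience with qualitative research and the rates of objective complications in the patients enrolled to date". It concludes: "Therefore, we will plan to randomize 70 - 140 patients". Recruitment is to run as far as feasible, up to year 5.

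On masking, section 3 (Blinding) says: "Participants will remain blinded to treatment arm until the Day 12 follow-up appointment".

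**The concern.** A primary outcome should be fixed before anyone sees the data it will be tested on. Here the plan itself gives the order of events: the data were examined, the objective measures were judged inadequate, and a different kind of data was then to be added to each primary measure. What would be tested as primary is left undefined. Without a definition, almost any later combination of laboratory values and interview material could be presented as the planned outcome.

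The added material is also more open to bias. Interview codes are developed from themes that emerge in a subset of this trial's own transcripts (section 3). Interviews at Week 6, Month 6 and 1 Year come from participants who have been told their arm. At stake is the one comparison for which the trial was sized, which rests on a laboratory value obtained while participants are masked.

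**Working it through.** **1. The plan's own figure, and what it covers.** Inputs from section 8.1: p1 = 0.12, p2 = 0.36, alpha 0.05, power 0.80. Sidedness is not stated; two-sided is assumed. The mean rate is 0.24 and the difference d is 0.24.

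- Uncorrected: n = [1.96 × √(2 × 0.24 × 0.76) + 0.8416 × √(0.12 × 0.88 + 0.36 × 0.64)]² / 0.24² = (1.1838 + 0.4878)² / 0.0576 = 48.5 per arm.
- Continuity-corrected: n' = (n/4) × [1 + √(1 + 4/(n × d))]² = 56.5, so 57 per arm and 114 in total.

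This is within two patients of the stated 116. Adding 20% gives 116 × 1.2 = 139.2, which matches 140. The calculation therefore supports the Day 1 endpoint only. No equivalent can be run for an outcome that includes interview data, because no score, effect size or variance is given.

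**2. The sections side by side.**

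| Place | What it says about the primary outcome |
|---|---|
| 2.1 | Day 1 PTH, later calcium and PTH, calcium intake, symptom frequency and severity, Month 6 supplement requirement. No interview item. |
| 2.2 | Interview themes and codes are listed under quality of life, as secondary. |
| 8.1, sizing | Primary endpoint at post-operative day 1. |
| 8.1, later text | Subjective data to enter each primary and secondary measure. |
| 8.2 | Mixed-model analysis of variance for all primary aims. No scoring or combining rule. Alpha adjustment promised but not specified. |

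The later text of 8.1 cannot be squared with the other four entries. Section 2.1 already holds patient-reported items, but these come from the symptom log kept over the first two weeks. The interviews are what would be new to the primary outcome.

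**3. Masking.** Day 1 PTH is measured before participants are told their arm. The Week 6, Month 6 and 1 Year interviews come afterwards. For the Day 12 interview, the documents do not say whether it precedes or follows disclosure at that visit.

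**4. How large could the effect be?** Suppose one of two versions of the primary outcome were chosen after seeing by-arm results, each tested at 0.05.

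- Independent versions: 1 − 0.95² = 0.0975, about 9.8%.
- Correlated test statistics (bivariate normal, correlations assumed for illustration): 9.1% at 0.5 and 7.8% at 0.8.

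Two measures of the same complication in the same patients would be correlated, so 9.8% is a ceiling for this two-version case.

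**The case against.** The strongest reply is that nothing has been redefined. The sentence is forward-looking, speaks of making the existing aims more robust, and left section 2.1 untouched. The stated purpose of the qualitative data is to see where objective and patient-reported evaluations differ, which compares ways of measuring and is not a new test of one arm against the other. This stands as far as it goes: the change is announced, not carried out. But the sentence is in the current text, it covers each primary measure, and the missing definition is what leaves it open.

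Second, the review of preliminary data may have been pooled over arms. The documents do not say. If it was pooled, error inflation would be smaller, though the change would still have been prompted by trial data.

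Third, the qualitative work has safeguards. Interviewers are not clinical staff, guides were piloted, transcripts are stripped of identifiers before coding, and developing codes from transcripts is ordinary practice. All of that is fair for a qualitative aim. None of it restores masking or prespecification for a confirmatory outcome.

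A reader might go further and infer that recruitment between 70 and 140 will stop when the result looks favourable, with the inflation that repeated testing brings. The documents do not support this. They contain no by-arm interim test and no efficacy stopping rule, the monitoring committee's power to suspend enrolment is tied to safety, and accrual is already limited to 140 randomised and to year 5. A reader might also infer that the interviews were favoured because they show a larger arm difference, or that the objective measures were found uninformative. The text says neither.

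**Conclusion.** The concern holds in a limited form. Section 8.1 announces a data-driven change to the primary outcome that conflicts with sections 2.1 and 2.2 and with its own sizing endpoint, and that section 8.2 cannot analyse. If followed, it would give a partly unmasked primary outcome whose coding comes from the trial's own transcripts.

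The amount of type I error inflation cannot be stated. The figure of about 9.8% applies only if one of two independent versions were selected on by-arm results at an unadjusted 0.05. It would be lower with correlated versions, a pooled review, or a properly applied version of the alpha adjustment that section 8.2 promises. That the new material is interview data is a reading of the sentences around the statement, though a natural one.

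This should be corrected before analysis. It falls short of a defect that must be cured for the trial to stand, because the section 2.1 definitions are still in place and can simply be confirmed.

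**What to change.** 1. In section 8.1, replace the sentence on incorporating subjective data. State that the section 2.1 definitions stand, that Day 1 PTH below 10 pg/ml (12% versus 36%) is the single confirmatory comparison, and that interview-derived measures are reported separately, as exploratory and added after data review. Make section 2.1 say the same.
2. Record when the preliminary data were examined, by whom, and whether by arm.
3. To the existing limits of 140 randomised and year 5, add one sentence: the point at which accrual ends is chosen without by-arm results.

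The cost is a few sentences. Interview results keep their place in the report but cannot support a confirmatory claim. The sponsor should also know that the confirmatory comparison would be weaker at the lower end of the range. With 35 per arm, power for 12% versus 36% is Φ[(0.24 × √35 − 1.1838) / 0.5797] = 0.66 by the uncorrected normal approximation, against 0.87 at 58 per arm by the same formula. That is a separate sample-size question, and this wording change does not settle it.
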